8.2. Enrollment

Once a subject has been deemed eligible as per Section 5.1 and Section 5.2, the subject should be enrolled into this study. For subjects choosing to continue treatment with pexidartinib, they will remain on their dosage level at the end of the prior study. For subjects choosing to enroll into the

Treatment-Free period of the **Treatment-Free/Re-Treatment Cohort**, pexidartinib treatment should be immediately stopped.

8.3. Efficacy Assessments

8.3.1. Response Assessment

Assess the subject based upon the local laboratory results using the Response Criteria (Section 10.4). Additional details will be available in the Study Laboratory Manual.

8.3.2. Patient Reported Outcomes

The PROMIS PF (Section 10.6.1) and EQ-ED-5L (Section 10.6.3) questionnaires will be used for PROs.

8.3.3. Radiographic Tumor Assessments

The Investigator will evaluate the MRI scans in order to perform a qualitative tumor assessment (i.e., stable disease). These data will be used to inform the Investigator and patient regarding the next steps in the course of treatment.

The Sponsor may retain the MRI scans to retrospectively evaluate the tumor response, by central radiographic readers, for study and non-study related purposes.

Individual subject outcomes by TVS will be classified according to the following criteria inspired by RECIST:

- Complete response: Lesion completely gone.
- Partial response: $\geq 50\%$ decrease in volume score relative to baseline.
- Progressive disease: $\geq 30\%$ increase in volume relative to lowest score during the study whether at baseline or some other visit.
- Stable disease: Does not meet any of the prior criteria based on score during study.

The cutoffs of 50% for partial response (PR) and $\geq 30\%$ for progressive disease (PD) were developed in consultation with clinical experts.

The TVS is a semi-quantitative MRI scoring system that describes tumor mass and is an extension of the 4-point synovitis scale of the well-established and widely used multi-feature score Rheumatoid Arthritis Magnetic Resonance Imaging (RAMRIS), originally developed for rheumatoid arthritis,⁸ and Whole-Organ Magnetic Resonance Imaging Score (WORMS), originally developed for osteoarthritis.⁹ The extended scale, the TVS, will be based on 10% increments of the estimated volume of the maximally distended synovial cavity or tendon sheath involved. Thus, a tumor that is equal in volume to that of a maximally distended synovial cavity or tendon sheath will be scored 10, whereas a tumor that is 70% of that volume will be scored 7, a tumor that is twice the volume of the maximally distended synovial cavity or tendon sheath will be scored 20, and so on. A score of “0” means no evidence of tumor.

Re-Treatment Assessment

At each visit, subjects who are in the Treatment-Free period will be assessed by the Investigator for pexidartinib re-treatment based on Investigator and subject's discretion.

8.4. Safety Assessments

8.4.1. Adverse Event

Methods to Detect Adverse Events

The definitions of an AE, TEAE, and SAE can be found in Section 9.5.2 and Section 10.5. Adverse events may be directly observed, reported spontaneously by the subject or by questioning the subject (or, when appropriate, by a caregiver, surrogate, or the subject's legally authorized representative) at each study visit. Subjects should be questioned in a general way, without asking about the occurrence of any specific symptoms. Between scheduled clinic visits, subjects should be instructed to enter all AEs in their Diary. The Investigator must assess all AEs to determine seriousness, severity, and causality. The Investigator and any qualified designees are responsible for detecting, documenting, and recording events that meet the definition of an AE or SAE and remain responsible for following AEs that are serious, considered related to the study drug or study procedures, or that caused the subject to discontinue pexidartinib.

All clinical laboratory results, vital signs, and ECG results or findings should be appraised by the Investigator to determine their clinical significance. Isolated abnormal laboratory results, vital sign findings, or ECG findings (i.e., not part of a reported diagnosis) should be reported as AEs if they are symptomatic, lead to study drug discontinuation, lead to dose reduction, require corrective treatment, or constitute an AE in the Investigator's clinical judgment.

COVID-19 assessments are detailed in Section 8.4.4.

Time Period for Collecting Adverse Events, Serious Adverse Events

All serious adverse events (SAEs) occurring after the subject signs the ICF and up to 30 days after the last dose of study medication if applicable or EOS/FU visit, whether observed by the Investigator or reported by the subject, will be recorded on the AE eCRF. All SAEs will be followed until resolution, stabilization, the event is otherwise explained, or the subject is lost to follow-up.

All non-serious AEs occurring after the subject has taken the first dose of study medication/signs the ICF until 30 days after the last dose of study medication will be recorded on the AE eCRF.

Exacerbation of a pre-existing medical condition and symptom after the subject signs the ICF including increase in severity of the symptom will be recorded as an AE on the AE eCRF, unless it is a condition of TGCT.

Reporting Procedure for Investigators

All AEs (including adverse events of special interest [AESIs] and SAEs) will be reported in the AE eCRF. All AEs (serious and non-serious) must be reported with the Investigator's assessment of seriousness, severity, and causality to pexidartinib.

Always report the diagnosis as the AE or SAE term. When a diagnosis is unavailable, report the primary sign or symptom as the AE or SAE term with additional details included in the narrative until the diagnosis becomes available. If the signs and symptoms are distinct and do not suggest a common diagnosis, report them as individual entries of AE or SAE.

Disease-Specific AEs and SAEs

Disease progression/worsening of TGCT will not be recorded as an AE on the Adverse Event eCRF. However, events associated with disease progression, may be recorded as AEs.

Death due to disease progression should be recorded on the Death eCRF.

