	Safety	
Title: Number of subjects with AE during the Treatment-Free period*
 
Description: Total number of subjects in the safety analysis set with any AE collected between Screening and start of re-treatment or final database lock (whichever occurs first)
 
Time frame: 24 months after last subject enrolled in the Cohort
 
*Note: Listed as a secondary objective but is a primary outcome measure.
	Incidence of AEs and SAEs, ECGs, and laboratory assessments	Safety
Re-Treatment period	Tumor Assessment	
Title: Tumor assessment
 
Description: Investigator evaluation of tumor
 
Time frame: 24 months after last subject enrolled in the Cohort
	Qualitative assessment of the tumor	Efficacy
	Change from Baseline in Patient Reported Outcomes (PROs)	
Title: Change from Baseline in PROs
 
Description: Change from Baseline in PROs (PROMIS PF, EQ-5D-5L)
 
Time frame: 24 months after last subject enrolled in the Cohort
	Mean change from Baseline* for PROMIS PF and EQ-5D-5L quarterly for the retreatment periods. *Note: Baseline is reinitiated with subject entering Re-Treatment period.	Efficacy
	Safety	
Title: Number of subjects with AE during the Re-Treatment period*
 
Description: Total number of subjects in the safety analysis set with any AE collected between first re-treatment dose and final database lock
 
Time frame: 24 months after last subject enrolled in the Cohort
 
*Note: Listed as a secondary objective but is a primary outcome measure.
	Incidence of TEAEs and SAEs, ECGs, and laboratory assessments	Safety

II. Treatment Continuation Cohort

Objectives	Outcome Measure	Endpoints	Category
Primary Objective			
None			
Secondary Objectives			
Tumor Assessment	
Title: Tumor assessment
 
Description: Investigator evaluation of tumor
 
Time frame: 24 months after last subject enrolled in the Cohort
	Qualitative assessment of the tumor	Efficacy
Change from Baseline in PROs	
Title: Change from Baseline in PROs
 
Description: Change from Baseline in PROs (PROMIS PF, EQ-5D-5L)
 
Time frame: 24 months after last subject enrolled in the Cohort
	Mean change from Baseline* for PROMIS PF and EQ-5D-5L at quarterly assessments. *Note: Baseline is Screening values.	Efficacy

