3. OBJECTIVES, OUTCOME MEASURES, AND ENDPOINTS

The objectives, definitions of associated endpoints, as well as applicable outcome measures are described in [Table 3.1](#) and [Table 3.2](#). Further requirements for the endpoint analyses and censoring rules, where applicable, can be found in [Section 9.5.1](#), [Section 9.5.2](#), and [Section 9.5.3](#).

Table 3.1: Description of Objectives, Outcome Measures, and Endpoints (Treatment-Free/Re-Treatment Cohort)

Period	Objectives	Outcome Measure	Endpoints	Category
Primary Objective				
Overall	Proportion of subjects who remain treatment-free	
Title: Proportion of treatment-free subjects at 12 months and 24 months
 
Description: Proportion of subjects who remain treatment-free at Month 12 and Month 24
 
Time frame: 24 months after last subject enrolled in the Cohort
	Proportion of subjects who remain treatment-free at Month 12 and Month 24	Efficacy
Secondary Objectives				
Treatment-Free period	Change from Baseline in Patient Reported Outcomes (PROs)	
Title: Change from Baseline in PROs
 
Description: Change from Baseline in PROs (PROMIS PF, EQ-5D-5L)
 
Time frame: 24 months after last subject enrolled in the Cohort
	Mean change from Baseline* for PROMIS PF and EQ-5D-5L quarterly for the treatment-free and Re-Treatment periods. *Note: Baseline is Screening values.	Efficacy
	Safety	
Title: Number of subjects with AE during the Treatment-Free period*
 
Description: Total number of subjects in the safety analysis set with any AE collected between Screening and start of re-treatment or final database lock (whichever occurs first)
 
Time frame: 24 months after last subject enrolled in the Cohort
 
*Note: Listed as a secondary objective but is a primary outcome measure.
	Incidence of AEs and SAEs, ECGs, and laboratory assessments	Safety
Re-Treatment period	Tumor Assessment	
Title: Tumor assessment
 
Description: Investigator evaluation of tumor
 
Time frame: 24 months after last subject enrolled in the Cohort
	Qualitative assessment of the tumor	Efficacy

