4.1.1. Design Overview

Subjects in the 4 ongoing TGCT studies will be screened at the "End-of-Treatment (EOT) visit" (i.e., the visit at which they receive their final dose of pexidartinib) of their previous study, at which time they can elect to enroll in the PL3397-A-U4003 study in 1 of 2 cohorts – the **Treatment Continuation Cohort** (where their existing pexidartinib treatment will continue uninterrupted) or **Treatment-Free/ Re-Treatment Cohort** (where they will discontinue pexidartinib treatment with the possibility to re-initiate treatment over the course of the study). Subjects who elect to not enroll in the PL3397-A-U4003 study will remain in their current study and complete their respective End-of-Study activities.

Subjects who elect to enroll in PL3397-A-U4003 will sign an institutional review board (IRB)/independent ethics committee (IEC)-approved informed consent form (ICF). By signing the ICF, subjects will permit acquisition and data transfer of any data collected in their precursor study, including, but not limited to, medical and surgical history, and prior medications. The assessments performed during the preceding study's End-of-Treatment visit will serve as the Baseline measurements for the PL3397-A-U4003 study.

Eligible subject who choose to continue pexidartinib treatment in the **Treatment Continuation Cohort** will remain on their current dosage regimen of pexidartinib and undergo clinical assessments at 3-month intervals for the duration of the study.

Subjects who choose to discontinue pexidartinib will be enrolled in the Treatment-Free period of the **Treatment-Free/Re-Treatment Cohort**. These subjects will stop pexidartinib dosing at entry into PL3397-A-U4003 (i.e., after their final dose at the preceding study's EOT visit). Subjects will undergo clinical assessments 1 month after enrollment, 3 months after enrollment, and then at 3-month intervals. Subjects will remain treatment-free until retreated with pexidartinib, based on the Investigator and/or subject's discretion. Considerations are given to tumor response, subjective and/or functional measures, and safety parameters in the decision-making process. The rationale for discontinuation and re-treatment with pexidartinib will be recorded accordingly.

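### Section 8.4.1 gives no usable end to non-serious AE recording for subjects off drug, and Section 9.5.2 omits the Treatment-Free AE count and the matching safety baseline

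*Combined protocol and SAP*

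**What the plan says.** Section 8.4.1 sets two collection periods. Serious events are recorded from consent "up to 30 days after the last dose of study medication if applicable or EOS/FU visit". Non-serious events are recorded from "first dose of study medication/signs the ICF until 30 days after the last dose of study medication will be recorded on the AE eCRF". Only the first has an end point that works without dosing.

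Section 4.1.1 says of the Treatment-Free period: "These subjects will stop pexidartinib dosing at entry into PL3397-A-U4003". Their final dose is given at the End-of-Treatment (EOT) visit of the preceding study.

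The synopsis and Table 3.1 define a safety outcome, "Number of subjects with AE during the Treatment-Free period", as the number of subjects in the safety set with "any AE collected between Screening and start of re-treatment or final database lock (whichever occurs first"). A note to this outcome in Table 3.1 reads "Listed as a secondary objective but is a primary outcome measure".

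Table 1.2 has an AE/SAE row, an AE diary reviewed up to Month 24, and a telephone call for AEs one month after the last visit. Section 8.4.1 also says "Between scheduled clinic visits, subjects should be instructed to enter all AEs in their Diary" and, under reporting, "All AEs (including adverse events of special interest [AESIs] and SAEs) will be reported in the AE eCRF".

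Section 9.5.2 defines TEAEs from the first dose of study drug to 30 days after the last. It assigns each AE to the period in which it began and plans counts of subjects with TEAEs and treatment-emergent SAEs. For AEs in general it plans listings, with a separate COVID-19 summary. Its laboratory, ECG and vital-sign baseline is the latest available value before study drug or treatment is first given. The synopsis and Section 4.1.1 instead make the prior study's EOT assessments the baseline, and the synopsis expressly includes safety parameters. The synopsis sets a new baseline on entry to re-treatment.

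**The concern.** The Treatment-Free period is the part of the study in which subjects are off drug by design, yet three safety rules are anchored to dosing: when non-serious AEs are recorded, which AEs are counted, and what change is measured from.

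The Treatment-Free outcome counts AEs that were collected, so it inherits whatever window sites apply. If sites differ on when recording ends, the count reflects site practice as well as what happened to subjects. A site that stopped at day 30 would lose later non-serious events permanently. The counting and baseline gaps are less serious, because a SAP finalised before database lock can close them.

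**Working it through.** The plan gives no sample size, event rate or test for this outcome, so there is no figure of its own to reproduce. The check compares the rules and adds day counts.

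**1. Recording window, subject never re-treated**

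Inputs: a month is 30 days (Table 1.2 note); Treatment-Free follow-up lasts up to 24 months (Section 4.1.4); the final prior-study dose falls on the day of Screening/Baseline (Section 4.1.1, Table 1.2), taken as day 0; the AE call comes one month after the last visit, ±7 days (Table 1.2).

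- Month 24 = 24 × 30 = day 720.
- AE follow-up call = 720 + 30 = about day 750.

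| | Prior-study dose counts as the last dose | It does not count |
|---|---|---|
| Window closes | Day 30 | No end stated in 8.4.1 |
| Share of Treatment-Free days covered | 30/720 = 4.2% | All |
| Gap from closure to the AE call | 750 − 30 = 720 days | Not defined |
| Scheduled visits after closure (M1, M3, M6, M9, M12, M15, M18, M21, M24) | 8 of 9 | None |

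Neither column matches the outcome in Table 3.1. The text leans towards the right-hand column: the SAE sentence says the last dose may not apply, and the non-serious sentence allows recording to start at consent. It does not settle the matter.

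**2. Recording window, subject re-treated**

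Once re-treatment begins, the last dose is a re-treatment dose and the window reaches back over the whole Treatment-Free period. That is known only in retrospect. No final data loss is claimed for these subjects.

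**3. Counting**

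Table 3.1 requires subjects with any AE in the Treatment-Free period. The planned counts in 9.5.2 start at first dose. If only doses in this study count, a subject never re-treated can have no TEAE. If prior-study doses count, the TEAE window closes at day 30, except for treatment-related events. Either way the named count is not among the tables. The period-assignment rule and the listing would help to derive it but do not specify it. Section 3 refers readers to Sections 9.5.1 to 9.5.3 for endpoint analyses, and 9.5.3 plans nothing further.

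**4. Baseline for laboratory, ECG and vital signs**

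| Subject | 9.5.2, doses in this study only | 9.5.2, prior-study doses count | Design (synopsis, 4.1.1) |
|---|---|---|---|
| Never re-treated | No anchor | Before the first prior-study dose | Prior-study EOT visit |
| Re-treated, Treatment-Free values | About BL-2, after the values it should precede | Before the first prior-study dose | Prior-study EOT visit |

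BL-2 is the intended baseline for the Re-Treatment period, so there is no conflict there, and none is claimed for the Treatment Continuation Cohort.

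**The case against.** The day-30 reading is strained. It treats a dose given in another study as this study's last dose, while the same sentence offers consent as a start date, which suits subjects with no dose here. On the other reading no days are excluded, and Table 1.2 supplies the end through its AE row, diary and follow-up call. A site stopping at day 30 would have to disregard all three. On counting, Table 3.1 already states the statistic, and Section 9.5 calls itself a summary with detail left to the SAP. On baseline, the specific rule in the synopsis and 4.1.1 can be read as overriding generic wording; Section 8.4.3 and Table 1.2 also allow prior-study values at Baseline. The study is descriptive, and 9.5.1.1 names only the treatment-free proportion as the primary endpoint.

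Much of this stands. The 4.2% is conditional on the weaker reading, and the outcome can be produced if sites follow Table 1.2. It limits the severity but does not remove the conflict. The sentence headed as the collection period still lacks an end that the sentence beside it has. Followed as written, 9.5.2 gives neither the named count nor the design's Treatment-Free baseline. A SAP can repair those two points, but it cannot restore events never entered.

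**Conclusion.** The concern holds on all three points, and the text should be corrected.

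- **Recording:** for a subject never re-treated, the window in 8.4.1 either covers 30 of up to 720 days (4.2%) or has no stated end. The percentage assumes full 24-month follow-up, a 30-day month, and that the prior-study dose counts. No AE rate is assumed, so no number of lost events is claimed.
- **Counting:** 9.5.2 has no table for an outcome that Table 3.1 calls primary.
- **Baseline:** the 9.5.2 rule does not give the prior-study EOT baseline for Treatment-Free values.

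The primary analysis in 9.5.1.1 and SAE collection are not affected.

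**What to change.** - **Section 8.4.1.** Give non-serious AEs the same end points as SAEs. State that in the Treatment-Free period recording runs from consent to the EOS/AE follow-up call or the start of re-treatment, after which the on-treatment window applies. State that the on-treatment window is unchanged.
- **Section 9.5.2 or SAP, counts.** Tabulate the number and percentage of subjects with any AE starting from Screening to the day before the first re-treatment dose or, if never re-treated, to the EOS/AE follow-up call. Tabulate TEAEs from the first re-treatment dose in the Re-Treatment Analysis Set, which Section 9.4 already assigns to re-treatment safety.
- **Section 9.5.2 or SAP, baseline.** Use the prior-study EOT visit for Treatment-Free laboratory, ECG and vital-sign changes, and BL-2 for the Re-Treatment period. The Treatment Continuation Cohort needs only consistent wording.

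The cost is one or two sentences in 8.4.1, some wording in 9.5.2 or the SAP, one extra table and slightly more AE data entry. The visits, diary and call already exist.

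The end point should not simply become EOS for everyone. Under Table 1.1 footnote e, early leavers on treatment without radiologic progression reach EOS after an MRI at 3 months ± 14 days from the last dose. That is 90 − 14 = 76 to 90 + 14 = 104 days or more, against the current 30.

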10.5. Appendix 5: General Information – Adverse Events

10.5.1. Definition of Adverse Event

An AE is any untoward medical occurrence in a subject administered a pharmaceutical product and that does not necessarily have to have a causal relationship with this treatment. An AE can therefore be any unfavorable and unintended sign (including an abnormal laboratory finding, for example), symptom, or disease temporally associated with the use of a medicinal product, whether or not considered related to the medicinal product.¹⁴

It is the responsibility of Investigators, based on their knowledge and experience, to determine those circumstances or abnormal laboratory findings which should be considered AEs.

Events Meeting the AE Definition

- Any abnormal laboratory test results (hematology, clinical chemistry, or urinalysis) or other safety assessments (e.g., ECG, radiological scans, vital signs measurements), including those that worsen from baseline, considered clinically relevant in the medical and scientific judgment of the Investigator (i.e., not related to progression of underlying disease).
- Exacerbation of a chronic or intermittent pre-existing condition including either an increase in frequency and/or intensity of the condition.
- New conditions detected or diagnosed after study intervention administration even though it may have been present before the start of the study.
- Signs, symptoms, or the clinical sequelae of a suspected drug-drug interaction.
- Signs, symptoms, or the clinical sequelae of a suspected overdose of either study intervention or a concomitant medication. Overdose per se will not be reported as an AE/SAE unless it is an intentional overdose taken with possible suicidal/self-harming intent. Such overdoses should be reported regardless of sequelae.

Events NOT Meeting the AE Definition

- Any clinically relevant abnormal laboratory findings or other abnormal safety assessments which are associated with the underlying disease, unless judged by the Investigator to be more severe than expected for the subject's condition.
- The disease/disorder being studied or expected progression, signs, or symptoms of the disease/disorder being studied, unless more severe than expected for the subject's condition.
- Medical or surgical procedure (e.g., endoscopy, appendectomy): the condition that leads to the procedure is the AE.
- Situations in which an untoward medical occurrence did not occur (social and/or convenience admission to a hospital).

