- “Lack of efficacy” or “failure of expected pharmacological action” per se will not be reported as an AE or SAE. Such instances will be captured in the efficacy

assessments. However, the signs, symptoms, and/or clinical sequelae resulting from lack of efficacy will be reported as AE or SAE if they fulfill the definition of an AE or SAE.

- Anticipated day-to-day fluctuations of pre-existing disease(s) or condition(s) present or detected at the start of the study that do not worsen.

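### Sections 8.4.1 and 10.5.1 disagree on when worsening TGCT signs and symptoms are AEs, so the Treatment-Free AE count, a primary outcome measure, can depend on which passage a site follows

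*Combined protocol and SAP*

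**What the plan says.** - Section 8.4.1, on the period for collecting AEs: worsening of a pre-existing condition or symptom after consent "will be recorded as an AE on the AE eCRF, unless it is a condition of TGCT". There is no severity test.
- Section 8.4.1, Disease-Specific AEs and SAEs: "Disease progression/worsening of TGCT will not be recorded as an AE on the Adverse Event eCRF", but "events associated with disease progression, may be recorded as AEs". No criterion follows.
- Section 10.5.1, events that meet the AE definition: "Exacerbation of a chronic or intermittent pre-existing condition including either an increase in frequency and/or intensity of the condition". This bullet has no TGCT exception.
- Section 10.5.1, events that do not meet the definition: "expected progression, signs, or symptoms of the disease/disorder being studied, unless more severe than expected", judged against the subject's condition.
- Section 10.5.1, on lack of efficacy: "the signs, symptoms, and/or clinical sequelae resulting from lack of efficacy will be reported as AE or SAE", provided that they meet the AE definition.
- Table 3.1 and the synopsis list "Number of subjects with AE during the Treatment-Free period" under a secondary objective, with a note that it is a primary outcome measure. Its window runs from Screening until re-treatment begins or the database is locked, whichever is first.
- Section 8.4.1 collects non-serious AEs only up to 30 days after the last dose. In the Treatment-Free period the last dose was the one at the prior study's End-of-Treatment visit (Section 4.1.1).

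**The concern.** Keeping disease worsening apart from drug toxicity is conventional when the drug is the exposure. In the Treatment-Free period the exposure is stopping the drug. Section 4.2 assumes that treatment can be suspended until signs of progression appear, so worsening TGCT is the foreseeable consequence of stopping. That is an inference from the design rationale; the protocol does not call it the main harm.

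Section 2.2 says that the study should inform safe as well as effective discontinuation, and the AE count is the safety measure for that period. If sites read the recording rule differently, part of the count reflects site practice. If all sites follow the flat exclusion, a subject can have clearly worse joint symptoms off drug and still be reported as having no AE.

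**Working it through.** The documents give no AE rate, cohort size or power calculation (Section 9.3 bases the sample size on eligibility alone), so there is no planned figure to reproduce. The check is a comparison of the rules on two cases.

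**Case A.** A Treatment-Free subject has worse joint pain and swelling than at Baseline on Day 20, not serious and inside the 30-day collection window.

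| Passage | Is it an AE? |
|---|---|
| 8.4.1, exacerbation rule | No, whatever the severity |
| 8.4.1, Disease-Specific AEs | Worsening itself: no. Associated events: optional |
| 10.5.1, excluded events | No if expected for the subject; yes if more severe |
| 10.5.1, lack of efficacy | Refers back to the AE definition, so adds no separate rule |

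Within 10.5.1, the general bullet on exacerbation can be reconciled with the more specific exclusion for the studied disease. What cannot be reconciled is the flat exclusion in 8.4.1 with the severity exception in 10.5.1, or either of them with an undefined option to record. Section 8.4.1 refers to Sections 9.5.2 and 10.5 for definitions and then states its own rule. No order of precedence is given.

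**Case B.** The same event at Month 4. With the schedule's 30-day month this is 4 × 30 = 120 days after the last dose. Read literally, the non-serious window in 8.4.1 closed at Day 30, so the event is not collected whichever TGCT rule applies. The Treatment-Free period can last 24 × 30 = 720 days, and the outcome in Table 3.1 covers all of it. Table 1.2 also provides a diary for AEs between visits throughout the period, so the literal window probably was not intended. It still has to be aligned, or changing the TGCT rule alone would not capture later events.

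**What other records show.** For Treatment-Free subjects the protocol also collects:
- PROs, MRI and a joint functional assessment at Month 1 and then quarterly (Table 1.2);
- concomitant treatment with its reason, and analgesics (6.6, 6.6.1);
- the rationale for re-treatment (4.1.1);
- re-treatment, other systemic therapy and surgery as primary-endpoint events (9.5.1.1).

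The planned summaries do not turn these into the missing number. PROs are reported as values and mean changes over time, and the tumour summary names only re-treated and Treatment Continuation subjects (9.5.1.2). Physical examination findings are listed (9.5.2). A subject who worsens but stays off drug, without surgery or other systemic therapy, has no event under 9.5.1.1.

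**Form of the effect (illustration; both rates are assumed).** Let b be the share of subjects with a non-TGCT AE and w the share with worsening TGCT symptoms, taken as independent and all collected. The share with any AE is b if TGCT symptoms are excluded and 1 − (1 − b)(1 − w) if included, a gap of w(1 − b).

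- b = 0.7, w = 0.2: 0.70 against 0.76, gap 0.06
- b = 0.5, w = 0.4: 0.50 against 0.70, gap 0.20
- b = 0.3, w = 0.6: 0.30 against 0.72, gap 0.42

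The gap is small when most subjects have another AE anyway and large when few do. The documents do not say which applies.

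**The case against.** The strongest reply is that the passages share a default: TGCT worsening is not an AE. Sections 8.4.1 and 10.5.1 then differ only in their exceptions. The protocol classes remaining treatment-free, PROs and tumour assessment as efficacy, so disease worsening is measured there by design, and the study is descriptive with no hypothesis test. This stands in part. Keeping progression itself off the AE form is not a fault. The fault is that the exceptions for its signs and symptoms differ and one of them is undefined.

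Three stronger readings are tempting, and the documents do not support them.

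- A reader might count the lack-of-efficacy sentence as a further rule that makes recording mandatory. It applies only if the AE definition is met, and lack of efficacy fits poorly when no drug is taken.
- A reader might infer that a flare between visits leaves no trace elsewhere. Medication records, joint examinations, PROs, MRI and primary-endpoint events will catch many. An untreated flare that resolves between visits could be missed.
- A reader might infer that the test in 10.5.1 cannot be applied off drug. Section 2.2 says only that data beyond 3 months are lacking to understand the impact of stopping fully. The Investigator can still judge against the subject's own condition, though subjectively.

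**Conclusion.** The inconsistency is in the current text and should be resolved. It affects a measure that the protocol labels primary, and it makes the classification of a subject whose only event is TGCT symptom worsening depend on the passage followed. Under the exacerbation rule in 8.4.1 such a subject is always left out.

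The size is unknown. The gap of 6 to 42 percentage points comes from assumed rates (b from 30% to 70%, w from 20% to 60%) and independence; it shows the mechanism and is not an estimate. It also presumes that events throughout the period are collected, which the literal 30-day window for non-serious AEs would prevent.

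The documents do not support the conclusion that stopping will be made to look safe overall, because other endpoints show part of the worsening. The supported conclusion is narrower: the AE count is not well defined for TGCT symptoms, and no planned summary supplies the number of Treatment-Free subjects who worsen symptomatically and stay off drug.

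**What to change.** 1. Put one rule in Section 8.4.1 (including Disease-Specific AEs and SAEs) and repeat it in 10.5.1: TGCT signs and symptoms that are new or worse than at this study's Baseline, or than at BL-2 after restart, go on the AE eCRF with a TGCT-related flag. Radiologic progression stays on the tumour form.
2. Align the non-serious AE window in 8.4.1 with the Treatment-Free outcome window in Table 3.1, so that events more than 30 days after the last dose are collected until re-treatment or database lock.
3. In Section 9.5.2, tabulate Treatment-Free AEs with and without flagged events. This must be a table of AEs: the subject counts now described there are of TEAEs, which end 30 days after the last dose unless treatment-related.

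The cost is protocol wording, one eCRF tick box and one extra table. The sponsor keeps its disease-excluded figure. The downside is that the Treatment-Free AE proportion including flagged events may look less favourable. No dosing or re-treatment rule changes.
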